3.3.2. Determination of the Phase 1b RP2D Regimen and Alternative Dosing Schedules

The RP2D of the erdafitinib/cetrelimab/platinum (cisplatin or carboplatin) chemotherapy combination will be determined after review of all available PK, PD, safety, and efficacy data from at least 6 subjects treated at the RP2D and the recommended dose by mTPI-2 design.

Alternative dosing strategies or schedules may be considered by the SET based on emerging data. The alternative dosing schedules, if explored, will be evaluated in a separate cohort distinct from dose escalation or dose expansion cohorts. The dose and schedule would be based on the totality of available data and decided by the SET.

Subjects who meet appropriate molecular eligibility criteria at the time the RP2D is selected and who have not had prior systemic treatment in the metastatic setting (ie, recurrence of tumor >12 months since last dose of chemotherapy for neo-adjuvant or adjuvant setting may be assigned 1:1 to the RP2D dose in consultation with the sponsor medical monitor if all other eligibility criteria are met.

Subject safety will be monitored as indicated in Section 3.4. Cumulative safety evaluation will be performed after completion of Cycle 2 therapy for all subjects in each dose level (DL2C, DL2C1, DL2D, and DL2D1).

3.4. Study Evaluation Team

Refer to Section 3.4 of the main body of the protocol.

4. SUBJECT POPULATION

Adult subjects age 18 years and older with metastatic or locally advanced urothelial cancer who meet the molecular eligibility and full-study eligibility are eligible for the study. Screening assessments will be performed as indicated in the Phase 1b erdafitinib + cetrelimab + platinum chemotherapy Table and Events schedule ([Appendix 2 Table 1](#)). Molecular eligibility assessment may occur ≥ 28 days prior to administration of the study drugs.

The inclusion and exclusion criteria for enrolling subjects in this study are described in the following 2 subsections. If there is a question about the inclusion or exclusion criteria below, the investigator should consult with the appropriate sponsor representative before enrolling a subject in the study. For a discussion of the statistical considerations of subject selection, refer to Section 11.1, Sample Size Determination.

4.1. Inclusion Criteria

Each potential subject must satisfy all of the following criteria to be enrolled in the study:

1. ≥ 18 years of age.
2.
 - Criterion modified per Amendment 2
 - 2.1 Histologic demonstration of transitional cell carcinoma of the urothelium. Variant urothelial carcinoma histologies such as glandular or squamous differentiation, or evolution to more aggressive phenotypes such as sarcomatoid or micropapillary change are acceptable.
 - 3.
 - Criterion modified per Amendment 2
 - 3.1 Metastatic or locally advanced urothelial cancer (Stage IV disease per AJCC Staging Guidelines)
 - 4.
 - Criterion modified per Amendment 2
 - 4.1 Criterion modified per Amendment 3
 - 4.2 Phase 1b erdafitinib + cetrelimab cohort and Phase 2: Meet appropriate molecular eligibility criteria. Tumors must have at least one gene fusion or gene mutation as defined in [Table 4](#).

Exception for Phase 1b erdafitinib + cetrelimab + platinum chemotherapy cohort: up to 3 subjects in each erdafitinib + cetrelimab + chemotherapy cohort at each dose level will be wild-type. Wild-type is defined as subjects without FGFR gene alteration and subjects with FGFR gene alterations other than the select FGFR alterations

described in [Table 4](#). All other subjects must have at least one select FGFR alteration as defined in [Table 4](#).

5. Criterion modified per Amendment 2

5.1 Must have measurable disease by radiological imaging according to the Response Evaluation Criteria in Solid Tumors (RECIST, version 1.1) at baseline.

6. Criterion modified per Amendment 2

6.1 Criterion modified per Amendment 3

6.2 Prior systemic therapy for metastatic urothelial cancer:

Phase 1b erdafitinib + cetrelimab cohort:

- Any number of lines of prior therapy

Renal function for subjects must have a creatinine clearance (CrCl) ≥ 30 mL/min as calculated by Cockcroft-Gault ([Attachment 8](#))

Phase 1b erdafitinib + cetrelimab + platinum chemotherapy cohort:

- No prior systemic therapy for metastatic disease. **Note:** Subjects who received neoadjuvant or adjuvant chemotherapy and showed disease progression, within 12 months of the last dose are considered to have received systemic chemotherapy in the metastatic setting
- Renal function for subjects must have a creatinine clearance (CrCl) ≥ 30 mL/min to receive carboplatin and ≥ 60 mL/min to receive cisplatin as calculated by Cockcroft-Gault ([Attachment 8](#))

Phase 2:

- No prior systemic therapy for metastatic disease. **Note:** Subjects who received neoadjuvant or adjuvant chemotherapy and showed disease progression, within 12 months of the last dose are considered to have received systemic chemotherapy in the metastatic setting
- Cisplatin-ineligible based on:
 - ECOG PS 0-1 AND at least one of the following criteria:
 - Renal function defined as creatinine clearance (CrCl) < 60 mL/min as calculated by Cockcroft-Gault ([Attachment 8](#)) ([Galsky 2011](#))
 - Grade 2 or higher peripheral neuropathy per NCI-CTCAE version 5.0.
 - Grade 2 or higher hearing loss per NCI-CTCAE version 5.0,

OR

- ECOG PS 2

7. Criterion modified per Amendment 2

7.1 Criterion modified per Amendment 3

7.2 ECOG PS Grade of (see [Attachment 3](#)) as defined below:

Phase 1b erdafitinib + cetrelimab cohort: ECOG 0-2

Phase 1b erdafitinib + cetrelimab + platinum chemotherapy cohort: ECOG 0-1 for cisplatin and 0-2 for carboplatin.

Phase 2: ECOG 0-2

8. Criterion modified per Amendment 1

8.1 Criterion modified per Amendment 2

8.2 Criterion modified per Amendment 3

8.3 Adequate organ function at Screening defined as follows:

Phase 1b erdafitinib + cetrelimab cohort and Phase 2

Hematology	
Bone marrow function (without the support of cytokines or erythropoiesis-stimulating agent in preceding 2 weeks)	
Hemoglobin	$\geq 8.0 \text{ g/dL} (\geq 5 \text{ mmol/L})$ (without transfusion or demonstrate stability, ie; no significant decline in hemoglobin, for 2 weeks after transfusion)
Platelets	$\geq 75 \times 10^9/\text{L}$
Absolute Neutrophil Count (ANC)	$\geq 1.5 \times 10^9/\text{L}$
Chemistry	
AST and ALT	$\leq 2.5 \times$ upper limit of normal (ULN) or $\leq 5 \times$ ULN for subjects with liver metastases
Creatinine clearance (mL/min)	Calculated using the Cockcroft-Gault formula (Attachment 8) Phase 1b erdafitinib + cetrelimab cohort: $\geq 30 \text{ mL/min}$ Phase 2: $\geq 30 \text{ mL/min}$. If the subject is considered cisplatin-ineligible based on creatinine clearance then CrCl must also be $< 60 \text{ mL/min}$.
Total bilirubin	$\leq 1.5 \times$ ULN or direct bilirubin \leq ULN for subjects with total bilirubin levels $> 1.5 \times$ ULN
Thyroid panel: TSH, T3 or Free T3 (FT3) and Free thyroxine (FT4)	All within normal range. If TSH is not within normal limits, the subject may still be eligible if total T3 or free T3 and free T4 are within normal limits.
Phosphate	Below institutional ULN within 14 days of treatment and prior to C1D1 (medical management allowed)
Cardiovascular	
Left ventricular ejection fraction	Within normal institutional limits
Abbreviations: ALT=alanine aminotransferase; ANC=absolute neutrophil count; AST=aspartate aminotransferase; QTcF=QT corrected interval by the Fridericia's formula; ULN=upper limit of normal	

Phase 1b erdafitinib + cetrelimab + platinum chemotherapy cohort

Hematology	
Bone marrow function (without the support of cytokines or erythropoiesis-stimulating agent in preceding 2 weeks)	
Hemoglobin	$\geq 9.0 \text{ g/dL (}\geq 5.59 \text{ mmol/L)}$ (without transfusion or demonstrate stability, ie; no significant decline in hemoglobin, for 2 weeks after transfusion)
Platelets	$\geq 100 \times 10^9/\text{L}$
Absolute Neutrophil Count (ANC)	$\geq 1.5 \times 10^9/\text{L}$
Chemistry	
AST and ALT	$\leq 2.5 \times$ upper limit of normal (ULN) or $\leq 5 \times$ ULN for subjects with liver metastases
Creatinine clearance (mL/min)	Calculated using the Cockcroft-Gault formula (Attachment 8) Phase 1b erdafitinib + cetrelimab + platinum chemotherapy cohort: $\geq 30 \text{ mL/min}$ to receive carboplatin and $\geq 60 \text{ mL/min}$ to receive cisplatin.
Total bilirubin	$\leq 1.5 \times$ ULN or direct bilirubin \leq ULN for subjects with total bilirubin levels $>1.5 \times$ ULN
Thyroid panel: TSH, T3 or Free T3 (FT3) and Free thyroxine (FT4)	All within normal range. If TSH is not within normal limits, the subject may still be eligible if total T3 or free T3 and free T4 are within normal limits.
Phosphate	Below institutional ULN within 14 days of treatment and prior to C1D1 (medical management allowed)
Cardiovascular	
Left ventricular ejection fraction	Within normal institutional limits

Abbreviations: ALT=alanine aminotransferase; ANC=absolute neutrophil count; AST=aspartate aminotransferase; QTcF=QT corrected interval by the Fridericia's formula; ULN=upper limit of normal

9. Criterion modified per Amendment 2

9.1 Criterion modified per Amendment 1.

9.2 Criterion modified per Amendment 3

9.3 Phase 1b erdafitinib + cetrelimab cohort and Phase 2:

Before the first dose of study drug:

Women of childbearing potential (defined as: fertile, following menarche and until becoming postmenopausal unless permanently sterile as a result of hysterectomy, bilateral salpingectomy, or bilateral oophorectomy) and fertile men who are sexually active must agree to use a highly effective method of contraception (<1%/year failure rate) during the study and for 5 months after the last dose of study drug. For men who are sexually active with women of childbearing potential: agree to use a condom with spermicidal foam/gel/film/cream/suppository during the study and for 5 months after the last dose of study drug. Contraception must be consistent with local regulations regarding the use of birth control methods for subjects participating in clinical trials. Women and men must agree not to donate eggs (ova,

oocytes) or sperm, respectively, during the study and for 5 months after the last dose of study drug.

Examples of highly effective methods include:

- user-independent methods: implantable progestogen-only hormone contraception associated with inhibition of ovulation; intrauterine device; intrauterine hormone-releasing system; vasectomized partner;
- user-dependent methods: combined (estrogen- and progestogen-containing) hormonal contraception associated with inhibition of ovulation: oral, intravaginal, and transdermal; progestogen-only hormone contraception associated with inhibition of ovulation: oral and injectable.

Note: If the childbearing potential changes after start of the study or the risk of pregnancy changes, a woman must begin a highly effective method of contraception, as described throughout the inclusion criteria. If reproductive status is questionable, additional evaluation should be considered. It should be noted that interaction between hormonal contraception and the combination of the study drugs have not been studied. Therefore, it is unknown whether the study drugs may reduce the efficacy of the contraceptive method.

- Sexual abstinence

(True sexual abstinence is considered a highly effective method only if defined as refraining from heterosexual intercourse during the entire period of risk associated with the study intervention. The reliability of true sexual abstinence needs to be evaluated in relation to the duration of the study and the preferred and usual lifestyle of the subject. Periodic abstinence [eg, calendar, ovulation, symptothermal, post-ovulation methods], declaration of abstinence for the duration of exposure to the study drugs, and withdrawal are not acceptable methods of contraception).

Phase 1b erdafitinib + cetrelimab + platinum chemotherapy cohort:

Before the first dose of study drug:

Women of childbearing potential (defined as: fertile, following menarche and until becoming post-menopausal unless permanently sterile as a result of hysterectomy, bilateral salpingectomy, or bilateral oophorectomy) and fertile men who are sexually active must agree to use a highly effective method of contraception (<1%/year failure rate) during the study and for 6 months after the last dose of study drug. For men who are sexually active with women of childbearing potential: agree to use a condom with spermicidal foam/gel/film/cream/suppository during the study and for 6 months after the last dose of study drug. Contraception must be consistent with local regulations regarding the use of birth control methods for subjects participating in clinical trials. Women and men must agree not to donate eggs (ova, oocytes) or sperm, respectively, during the study and for 6 months after the last dose of study drug.

Examples of highly effective methods include:

- user-independent methods: implantable progestogen-only hormone contraception associated with inhibition of ovulation; intrauterine device; intrauterine hormone-releasing system; vasectomized partner;
- user-dependent methods: combined (estrogen- and progestogen-containing)

hormonal contraception associated with inhibition of ovulation: oral, intravaginal, and transdermal; progestogen-only hormone contraception associated with inhibition of ovulation: oral and injectable.

Note: If the childbearing potential changes after start of the study or the risk of pregnancy changes, a woman must begin a highly effective method of contraception, as described throughout the inclusion criteria. If reproductive status is questionable, additional evaluation should be considered. It should be noted that interaction between hormonal contraception and the combination of the study drugs have not been studied. Therefore, it is unknown whether the study drugs may reduce the efficacy of the contraceptive method.

– Sexual abstinence

(True sexual abstinence is considered a highly effective method only if defined as refraining from heterosexual intercourse during the entire period of risk associated with the study intervention. The reliability of true sexual abstinence needs to be evaluated in relation to the duration of the study and the preferred and usual lifestyle of the subject. Periodic abstinence [eg, calendar, ovulation, symptothermal, post-ovulation methods], declaration of abstinence for the duration of exposure to the study drugs, and withdrawal are not acceptable methods of contraception).

10. Women of childbearing potential must have a negative pregnancy test at Screening within ≤ 7 days of C1D1 (first dose of study drug) using a highly sensitive pregnancy test (serum β -human chorionic gonadotropin [β -hCG]); see Section 9.6.4).
11. Sign an informed consent form indicating that he or she understands the purpose of and procedures required for the study, and is willing and able to participate in the study. Consent is to be obtained prior to the initiation of any study-related tests or procedures that are not part of standard of care for the subject's disease.
12. Willing and able to adhere to the prohibitions and restrictions specified in this protocol.

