Note: Subjects with vitiligo or resolved childhood asthma/atopy would be an exception to this rule. Subjects that require intermittent use of bronchodilators or local steroid injections would not be excluded from the study. Subjects with hypothyroidism stable on hormone replacement will not be excluded from the study. Subjects with a history of transient autoimmune manifestations of an acute infectious disease that resolved upon treatment of the infectious agent (eg, acute Lyme arthritis) will not be excluded from the study.

- Grade 3 or higher toxicity effects from previous treatment with immunotherapy.
- Psychiatric conditions (eg, alcohol or drug abuse), dementia, or altered mental status.
- Any other issue that would impair the ability of the subject to receive or tolerate the planned treatment at the investigational site, to understand informed consent or any condition for which, in the opinion of the investigator, participation would not be in the best interest of the subject (eg, compromise the well-being) or that could prevent, limit, or confound the protocol-specified assessments.

11. Pulmonary compromise requiring supplemental oxygen use to maintain adequate oxygenation.
12. Active or chronic hepatitis B or hepatitis C disease as determined by hepatitis B surface antigen (HBsAg), hepatitis B core antibody, or hepatitis C antibody (anti-HCV) positivity at Screening. If positive, further testing of quantitative levels to rule out active infection is required (see [Attachment 2](#)).

13. Criterion modified per Amendment 3

13.1 Phase 1b erdafitinib + cetrelimab and **Phase 1b erdafitinib + cetrelimab + platinum chemotherapy cohort:** Not recovered from reversible toxicity of prior anticancer therapy (except toxicities which are considered by the investigator as not clinically significant, such as alopecia, skin discoloration, or Grade 1 hearing loss or neuropathy).

Phase 2: Not recovered from reversible toxicity of prior anticancer therapy (except toxicities which are considered by the investigator as not clinically significant such as alopecia, or skin discoloration).

14. Impaired wound healing capacity defined as skin/decubitus ulcers, chronic leg ulcers, known gastric ulcers, or unhealed incisions.
15. Criterion modified per Amendment 2

15.1 Allergies, hypersensitivity, or intolerance to protein-based therapies or with a history of any significant drug allergy (such as anaphylaxis, hepatotoxicity, or

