5. TREATMENT ALLOCATION AND BLINDING

This is an open-label study. No blinding procedures will be applied.

Subjects will be enrolled sequentially to a dose level after a discussion between the investigator and the sponsor.

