6.4. Administration of Platinum Chemotherapy (Cisplatin or Carboplatin)

Standard chemotherapeutic agents will be prepared and administered as per the approved product label at the doses indicated below.

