Appendix 2 Table 7 : Dose Modifications for Cisplatin and Carboplatin

Category	Cisplatin		Carboplatin	
Starting dose	50 mg/m ²	60 mg/m ²	AUC 4 mg/mL/min (maximum dose 600 mg)	AUC 5 mg/mL/min (maximum dose 750 mg)
1st dose modification	Stop cisplatin but continue erdafitinib+ cetrelimab	50 mg/m ²	Stop carboplatin but continue erdafitinib+ cetrelimab	AUC 4.5 mg/mL/min (maximum dose 675 mg)
2nd dose modification	N/A	Stop cisplatin but continue erdafitinib+ cetrelimab	N/A	Stop carboplatin but continue erdafitinib+ cetrelimab

Creatinine clearance (CrCl)

CrCl will be based on the original weight-based Cockcroft and Gault formula ([Attachment 8](#)). The subject's CrCl at Screening must be ≥ 30 mL/min to receive carboplatin and ≥ 60 mL/min to receive cisplatin prior to each cycle of platinum chemotherapy. Cisplatin may be delayed for up to 21 days (1 cycle) to allow the subject time to recover from the toxicity. If a subject's CrCl value has not returned to ≥ 30 mL/min within 42 days (2 cycles) after the previous dose, cisplatin must be discontinued.

In general, study drug(s) should be held for AEs \geq Grade 3 that are not attributable to erdafitinib, cetrelimab, platinum chemotherapy, or the disease under study. If the event resolves to Grade 1 or baseline within 4 weeks, platinum chemotherapy and erdafitinib may be reintroduced at one dose level lower. If the same toxicity does not recur or worsen within 4 weeks after re-starting therapy, then cetrelimab may be reintroduced at the same dose. Following re-introduction of study drugs, if the same AE recurs at \geq Grade 3 or there is a second incidence of a \geq Grade 3 event that is not attributable to erdafitinib, cetrelimab, platinum chemotherapy, or the disease under study, study drugs should be permanently discontinued.

For toxicity associated with platinum chemotherapy, the AE must resolve to Grade ≤ 1 or baseline prior to starting subsequent cycle. For individual subjects requiring a dose modification, treatment

for each new cycle may be delayed if the scheduled off-drug periods are not adequate to allow for recovery to Grade ≤ 1 or the baseline status of the subject.

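### Cisplatin levels DL2C and DL2C1 have no graded entry limit on neuropathy or hearing loss, except for unrecovered reversible toxicity of prior anticancer therapy

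*Protocol*

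**What the plan says.** **Entry limits for cisplatin.** In Appendix 2, section 4.1, criterion 7.2 sets "ECOG 0-1 for cisplatin and 0-2 for carboplatin". Criterion 6.2 requires a creatinine clearance of at least 60 mL/min "to receive cisplatin as calculated by Cockcroft-Gault", against 30 mL/min for carboplatin, and criterion 8.3 repeats those limits. No other inclusion criterion separates the two drugs. Criterion 6.2 also lists neuropathy and hearing loss of Grade 2 or above, but under its Phase 2 entry, where they are ways to qualify as cisplatin-ineligible.

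**Exclusions (section 4.2).** Criterion 13.1 bars subjects who have not recovered from reversible toxicity of earlier anticancer treatment. It excepts effects judged not clinically significant, "such as alopecia, skin discoloration, or Grade 1 hearing loss or neuropathy". Criterion 10 includes "Any other issue that would impair the ability of the subject to receive or tolerate the planned treatment at the investigational site". Criterion 2.1 allows earlier neoadjuvant or adjuvant chemotherapy if it ended more than 12 months before recurrence and was not stopped for drug toxicity.

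**Other safeguards.** Section 5 says "Subjects will be enrolled sequentially to a dose level after a discussion between the investigator and the sponsor". Section 6.4 says "Standard chemotherapeutic agents will be prepared and administered as per the approved product label at the doses indicated below".

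**Rules on treatment.** Appendix 2 Table 6 recommends two modification steps for cisplatin, and none for carboplatin, when neurotoxicity reaches Grade 2. In Table 7 the last cisplatin step at each level is "Stop cisplatin but continue erdafitinib+ cetrelimab".

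**The protocol's view of cisplatin fitness.** Section 1.6 gives neuropathy and severe hearing loss, without grades, among reasons why cisplatin cannot be given. Section 1.7, in the Phase 2 rationale, says that either condition at Grade 2 or above typically rules cisplatin out. The Synopsis and Appendix 3 criterion 6.2 make this the formal Phase 2 definition.

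**The concern.** The protocol uses four tests of cisplatin fitness: renal function, performance status, neuropathy and hearing. Where it defines patients who must not receive cisplatin (Phase 2), it uses all four. Where it enrols patients who will receive cisplatin (DL2C and DL2C1), it turns only two into explicit limits. The other two concern the toxicities of most relevance here: Table 6 is stricter for cisplatin than for carboplatin on neurotoxicity, and section 6.4.5 calls ototoxicity cumulative.

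At stake is mainly avoidable harm to a subject who enters with a Grade 2 deficit and worsens on cisplatin, when carboplatin levels are open in the same cohort. A secondary matter is reading the DLTs: a Grade 3 event that is one step up from a Grade 2 baseline says less about the dose than a new Grade 3 event does.

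**Working it through.** The check is a comparison of texts and a table lookup; the plan states no figure to reproduce.

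**1. The four fitness tests, Phase 2 definition against cisplatin entry.**

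| Test | Phase 2: cisplatin-ineligible if | Appendix 2: explicit limit for DL2C/DL2C1 |
|---|---|---|
| Creatinine clearance | below 60 mL/min | at least 60 mL/min |
| ECOG | 2 | 0-1 |
| Peripheral neuropathy | Grade 2 or above | none beyond exclusion 13.1 |
| Hearing loss | Grade 2 or above | none beyond exclusion 13.1 |

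The first two rows mirror each other exactly. The last two do not.

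**2. What exclusion 13.1 leaves open.** It applies only if the deficit (a) comes from prior anticancer therapy and (b) is reversible. Diabetic neuropathy and age-related hearing loss fail (a). A permanent deficit after adjuvant chemotherapy that was completed, and followed by recurrence more than 12 months later, fails (b) and passes exclusion 2.1. For these subjects, exclusion 10, the investigator-sponsor discussion and the product label remain. None of them states a grade in this document.

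**3. Test case.** ECOG 1, clearance 70 mL/min, Grade 2 diabetic neuropathy (an assumed patient). Phase 2 definition: cisplatin-ineligible. Graded limits for DL2C: all met.

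**4. Table 6 mapped onto Table 7, neurotoxicity on cisplatin.**
- Grade 2 = two modification steps.
- Start 50 mg/m² (DL2C): the first step is already stop.
- Start 60 mg/m² (DL2C1): first step 50 mg/m², second step stop.
- Grade 3 or 4: discontinue.
- Carboplatin, Grade 2: no modification at either level.

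So Grade 2 arising on treatment leads to a recommended stop at 2 of 2 cisplatin levels and no change at 2 of 2 carboplatin levels.

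**5. Hearing.** Section 6.4.6 with Table 8 requires platinum to stop if Grade 3 ototoxicity has not resolved to Grade 1 or less within 7 days. The next-cycle rule in section 6.4.4 accepts Grade 1 or less "or baseline prior to starting subsequent cycle"; the 6.4.6 rule has no such baseline clause. A subject with Grade 2 hearing loss at entry who worsens to Grade 3 would have to recover to better than baseline to stay on cisplatin.

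**6. Effect on escalation.** Appendix 2 Table 3 counts any Grade 3 non-hematological event as a DLT. Neuropathy and hearing loss are not among its exceptions, and there is no baseline adjustment. From a Grade 2 baseline, 3 − 2 = 1 grade of worsening is a DLT. Attachment 1, row for 1 DLT: n = 3 gives Stay; n = 4 to 9 gives Escalate. One further DLT-free subject reverses the Stay.

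**7. Exposure and numbers.**
- DLT window: 42 days / 21 days per cycle = 2 doses, so 2 × 50 = 100 to 2 × 60 = 120 mg/m².
- Maximum of 4 cycles: 4 × 50 = 200 to 4 × 60 = 240 mg/m².
- Planned cisplatin subjects: 3 + 6 + about 10 = about 19.
- Number with a baseline Grade 2 or higher deficit: not given.

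**The case against.** The strongest reply is that such patients are already screened out. Exclusion 13.1 names both toxicities and gives only Grade 1 as tolerable, so unrecovered reversible Grade 2 neuropathy or hearing loss from earlier cancer treatment is generally excluded. For the rest, exclusion 10 asks whether the subject can tolerate the planned treatment, which here is cisplatin; the sponsor discusses each assignment; and the drug is given per its label. Relying on judgement and the label is a legitimate design choice. This stands in part: there is cover, but it carries no grade in this document, and the label is not at hand to show how far it reaches.

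The reply also limits several stronger inferences that a reader might draw.

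- *That Appendix 2 admits any pre-existing Grade 2 neuropathy and has no hearing limit at all.* Exclusion 13.1 contradicts this.
- *That the entry and treatment rules formally contradict each other.* They do not. Table 6 addresses toxicity experienced during a cycle; section 6.4.4 calls Tables 5 and 6 a guide that does not replace judgement; and a stable deficit of another cause is not an adverse event. The graded ineligibility definition is formally for Phase 2, and section 1.7 says only what is typical.
- *That an entry deficit could hold the cisplatin dose.* The Stay applies at three subjects only, and at DL2C1, with six planned, 1 in 6 is already Escalate. The Study Evaluation Team also weighs all available data.
- *That cisplatin recipients get no audiometry.* One sentence in the cisplatin paragraph of section 6.4.5 is wrongly tied to cis-ineligible subjects, but the next provides for audiometry when clinically indicated. This is a wording slip.

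**Conclusion.** The point holds in a limited form. Beyond exclusion 13.1 and the ungraded exclusion 10, Appendix 2 sets no graded limit on neuropathy or hearing loss for cisplatin. Deficits of Grade 2 or above that have another cause, or are irreversible, pass every graded entry limit, although the protocol's own Phase 2 cut-off calls such patients cisplatin-ineligible and Tables 6 and 7 recommend stopping when neurotoxicity of that grade arises on treatment.

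The weight is on patient safety. The effect on dose-finding is minor and temporary, and the missing baseline clause in section 6.4.6 matters only to someone who worsens to Grade 3 and returns to Grade 2. The number affected among about 19 planned subjects is unknown and may be small. The conclusion assumes that the Phase 2 cut-off reflects the sponsor's general view of cisplatin fitness, as sections 1.6 and 1.7 suggest without stating it as a rule for this cohort. It is a cheap improvement to the design; the documents do not show that any result would be invalid without it.

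**What to change.** In Appendix 2, criterion 6.2 or 7.2, add for DL2C and DL2C1 only: *no Grade ≥2 peripheral neuropathy and no Grade ≥2 hearing loss (NCI-CTCAE v5.0)*. Judge this from the medical history and physical examination already scheduled at screening and from any existing audiometry or hearing-aid use, with no new mandatory test. Direct otherwise eligible subjects to the carboplatin levels. As a minor correction, remove the cis-ineligible audiometry sentence from the cisplatin paragraph of section 6.4.5 and keep audiometry as clinically indicated.

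The document does not say whether enrolment to these levels is still open. If it has closed, flag DL2C and DL2C1 subjects with a baseline Grade 2 or higher deficit when interpreting DLTs, neurotoxicity and ototoxicity.

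The cost is one line of amendment text. The downside is that a few candidates move from cisplatin to carboplatin.
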